1.0 PROTOCOL SUMMARY AND/OR SCHEMA

This is a phase 2, open-label, non-randomized study evaluating the novel combination of pembrolizumab and olaparib (POLAR) for maintenance therapy in three cohorts of metastatic PDAC patients with homologous recombination deficiency (HRD) in the first-line or second-line on-platinum setting; two cohorts are genomically enriched and one cohort is identified by platinum sensitivity. The primary endpoint of this study is to evaluate the co-primary endpoints using either 6-month progression-free survival (PFS) rate and objective response rate (ORR) of this combination. The secondary endpoints of this study are overall survival (OS), progression-free survival (PFS), disease control rate (DCR), CA 19-9, and CEA response. Statistically powered analysis of co-primary endpoints will be assessed in Cohort A only and other clinical endpoints will be descriptive in Cohort B and C. Exploratory scientific correlates include assessments of HRD genetic mutational signatures, neoantigens, immunogenic tumor microenvironment, and clonal evolutionary dynamics to study heterogeneity and resistance mechanism to POLAR.

Patients will be assigned to cohorts. Cohorts will be defined as following by CLIA-approved NGS or MSK-IMPACT Part A or C:

[figure not shown]
- **Cohort A**: Patients with either pathogenic germline or somatic alterations of 3 core homologous recombination-genes (HR-genes) (*BRCA1/2*, or *PALB2*) who have stable or responding disease on first-line or second-line platinum therapy in two consecutive imaging assessments over at least 4 months or 16 weeks are eligible for inclusion in Cohort A.
- Cohort B: Patients with either pathogenic somatic or germline non-core 15 HR-gene alterations (ATM, BAP1, BARD1, BLM, BRIP1, CHEK2, FAM175A, FANCA, FANCC, MUTYH, NBN, RAD50, RAD51, RAD51C, RTEL1) who have stable or responding disease on first-line or second-line platinum therapy in two consecutive imaging assessments over at least 4 months are eligible for inclusion in Cohort B.

POLAR: a phase 2 trial for pembrolizumab and olaparib maintenance for metastatic PDAC and HRD and/or Exceptional Response to Platinum – Ver. 5/3/2020

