2.0 OBJECTIVES AND SCIENTIFIC AIMS

Primary Objective:

- For Cohort A: To evaluate the activity of pembrolizumab and olaparib (POLAR) combination by co-primary endpoints using either radiographic 6-month PFS rate by RECIST v1.1 and ORR using iRECIST in metastatic pancreas adenocarcinoma (PDAC) patients with core HR-gene mutations.
- For Cohort B and C: To exploratively evaluate the activity of POLAR combination by radiographic ORR using RECIST 1.1.

Secondary Objectives:

- To assess the safety of POLAR by grading adverse events (AE) using CTCAE v. 5.0.
- To assess activity of POLAR by measuring disease control rate (DCR) by both RECIST v1.1 and iRECIST, best overall response rate (BOR), progression-free survival (PFS) by both RECIST v1.1 and iRECIST, overall survival (OS), CEA, and CA 19-9 response. Progression-free survival (PFS) will be analyzed from both the consent date and treatment start date (C1D1) (Reference study POLO defined PFS from the time of randomization not from C1D1, Golan 2019 NEJM).

Exploratory Objectives:

- To explore genetic and transcriptomic signatures for POLAR sensitivity and resistance from HRD Cohort A and B as well as from the platinum-sensitivity Cohort C.
- To describe neoantigen induction, the immunogenic tumor microenvironment (TME), and describe putative immunomodulatory targets from each cohort.
- To explore resistance mechanisms and the role of spatiotemporal heterogeneity by evaluating the tumor samples and circulating tumor DNA (MSK-ACCESS)
- To develop a biorepository of organoids and prospectively evaluate organoids concurrently with the trial in select patients.
- To assess second progression-free survival (PFS2) from time of subsequent systemic treatment start post-POLAR to progression on that treatment.
- To assess duration of the first-line or second-line treatment prior to POLAR treatment.
- To assess genetic signatures and compare clinical outcomes (ORR, PFS, OS) for patients with PDAC harboring specific HRD-gene mutations such as BRCA1, BRCA2, PALB2, ATM, and no HRD-gene mutation.
- To assess the association of other non-HRD gene mutations (such as KRAS allelic imbalance, TP53, SMAD4, CDKN2A homozygous deletion) with the clinical outcomes.
- Evaluate reversion mutation, zygosity, plasticity, and aneuploidy from tumor and circulating tumor DNA.

Confidential

POLAR: a phase 2 trial for pembrolizumab and olaparib maintenance for metastatic PDAC and HRD and/or Exceptional Response to Platinum – Ver. 5/3/2020

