All the participants will be enrolled on #12-245 and #06-107 outside of this trial which will allow identification of which Cohort the patient will be assigned to and to permit future biospecimen use for research. Patients have a germline or somatic HR-gene alterations identified in an external CLIA or FDA-approved NGS panel including but not limited to, FoundationOne, Myriad, or Tempus, will be eligible. After enrollment, we will retrospectively confirm their HR-gene alteration status from both germline and somatic MSK-IMPACT profiling.

Study Endpoints:

POLAR: a phase 2 trial for pembrolizumab and olaparib maintenance for metastatic PDAC and HRD and/or Exceptional Response to Platinum – Ver. 5/3/2020

- 1
- Primary endpoint: co-primary endpoints using either 6-month PFS rate by RECIST v1.1 and ORR by iRECIST as Figure 1. Schema.
- Secondary endpoints: disease control rate (DCR) by both RECIST v1.1 and iRECIST, best overall response (BOR), duration of response (DOR), PFS by both RECIST v1.1 and iRECIST, and OS. Biochemical markers (CEA, and CA 19-9 response). The safety of pembrolizumab and olaparib, toxicity grading by grading adverse events (AE) using CTCAE v. 5.0. To note, progression-free survival (PFS) will be analyzed from both the consent date and treatment start date (C1D1) (Reference study POLO defined PFS from the time of randomization not from C1D1, Golan 2019 NEJM).
- Exploratory endpoints: circulating tumor DNA by MSK-ACCESS, second progression-free survival (PFS2) from time of subsequent systemic treatment start post-POLAR to progression on that treatment, and duration of the first-line or second-line treatment prior to POLAR treatment. To also assess genetic signatures and compare clinical outcomes, evaluate reversion mutation, zygosity, plasticity and aneuploidy from tumor and ctDNA, and to assess the role of maintenance treatment with minimally residual disease by the presence of ctDNA and CA 19-9 and its trend prior to treatment.
- Correlative endpoints: Detailed objectives are in Section 4.3 Biomarker Assessments
- Explore HRD genetic signatures.
- Neoantigen surrogates (different mutation types, MHC I and II types, microbiome signatures). Peripheral blood and tumor immunoprofiling, T-cell receptor sequencing, transcriptomic, and proteomic analysis. Differential expression of immunologic gene and tissue protein.
- Intra/intertumoral heterogeneity and correlation of ctDNA to study early detection of resistance emergence.

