13.0 CRITERIA FOR OUTCOME ASSESSMENT AND ENDPOINT EVALUABILITY

13.1. Tumor Measurements

Response Evaluation Criteria in Solid Tumors (RECIST) version 1.1 will be used to determine treatment response. Baseline tumor measurements will be performed prior to initiation of therapy. These measurements should be done according to iRECIST (see Appendix 2) ⁵⁴. An estimate of overall objective and subjective response will be made and recorded at the end of treatment at 8 weeks after the last infusion. Since it is expected that immune activity would lead to tumor flare, the restaging CT scans may be repeated 8 weeks later based on irRECIST and the designation of iCR, iPR, iSD, iUPD, or iCPD will be made at that time. Best overall response will be used.

- **13.1.2.** Disease control rate (DCR): DCR is defined as the percentage of patients who have achieved complete response, partial response, and stable disease to the study treatment.
- **13.1.3.** Overall response rate (ORR): ORR is defined as the percentage of patients who have achieved complete response and partial response to the study treatment.
- **13.1.4. Best Overall Response (BOR):** BOR is defined as the best response recorded from the start of the study treatment until the disease progression/recurrence.
- **13.1.5.** Durable response rate (DRR): DRR is defined as the percentage of patients who had achieved continued disease responses (CR and PR) for more than 6 months.
- **13.1.6.** Durable disease control rate (DDCR): DDCR is defined as the percentage of patients who had achieved continued disease controls (CR, PR, and SD) for more than 6 months from the time from the initiation of study treatment.
- **13.1.7. Additional Assessments.** All patients will have a baseline tumor marker assessment and testing of tumor markers at the designated follow-up time points. Changes in serial tumor marker measurements, in those patients who have baseline elevations, will be utilized as a surrogate marker of clinical response, stable disease or disease progression and reported as such.
- **13.1.8. Patients without residual disease:** For patients whose primary tumor or metastatic disease has been removed or successfully treated, respectively, prior to entry into this trial, progression free survival will be evaluated based on duration of relapse-free survival.
- **13.1.9. Progression free survival (PFS):** PFS is defined as the time from the initiation of study treatment to radiographic progression or death.

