14.0 BIOSTATISTICS

This is a phase 2, open-label, non-randomized study evaluating the novel combination of pembrolizumab and olaparib (POLAR) in three cohorts of metastatic PDAC s with homologous recombination deficiency (HRD) in the first-line or second-line on-platinum maintenance setting, two of which are genomically enriched and one is identified by platinum sensitivity. The primary objective of the study is to determine both the 6-month PFS rate by RECIST v1.1 as well as the objective response rate (ORR, CR+PR) by iRECIST for this combination. Both factors will be considered for purposes of sample size determination as follows and a two-stage design will be employed. The secondary endpoints of this study are overall survival (OS), progression-free survival (PFS) by both RECIST v1.1 and iRECIST, disease control rate (DCR) by both RECIST v1.1 and iRECIST, CA 19-9, and CEA response. Progression-free survival (PFS) will be analyzed from both the consent date and treatment start date (C1D1), separately, due to the maintenance trial design. Exploratory scientific correlates include assessments of HRD genetic mutational signatures, neoantigens, immunogenic tumor microenvironment, clonal evolutionary dynamics to study heterogeneity, andresistance mechanism to POLAR. Exploratory endpoints will also include second progressionfree survival (PFS2) from time of subsequent systemic treatment start post-POLAR to progression on that treatment as well as assess duration of the first-line or second-line treatment prior to POLAR treatment. Exploratory endpoints will also assess genetic signatures and compare clinical outcomes, evaluate reversion mutation, zygosity, plasticity and aneuploidy from tumor and ctDNA, and to assess the role of maintenance treatment with minimally residual disease by the presence of ctDNA and CA 19-9 and its trend prior to treatment.

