evaluation and who did not respond or do not have documented response before their being lost to follow up will be counted as events (nonresponders/progressors) for the composite primary endpoint. However this will be uncommon. If after the first stage we meet the rule of observing 6 or more responses out of the 20 patients enrolled in the first stage, then no waiting is required and we can proceed with enrollment to the second stage. However, if we do not observe 6 out of 20 responses after the first stage, we will halt accrual after the first 20 patients until we obtain the 6-month PFS status for these 20 patients. The interim look for Cohort A will not affect accrual to Cohorts B and C.

Cohorts B and C will be exploratory and will enroll 15 patients each. ORR will be estimated using the binomial distribution along with exact 95% confidence intervals. With 15 accrued patients, we can estimate the DCR to within +/- 25% margins of error with 95% confidence.

Secondary objectives

Adverse events will be summarized descriptively and tabulated separately for each cohort. DCR will be estimated using binomial proportions along with exact 95% confidence intervals while PFS and OS will be estimated using the Kaplan-Meier method separately for each of the 3 cohorts. CEA and CA 19-9 will be summarized using medians and interquartile range.

Exploratory objectives

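### CA 19-9 and CEA response is a secondary endpoint built on serial change in patients with elevated baselines, but section 14.0 specifies only medians and interquartile ranges, which cannot yield a response rate

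*Protocol*

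**What the plan says.** Marker response appears among the secondary objectives or endpoints four times: in the protocol summary (1.0), in the objectives (2.0, "overall survival (OS), CEA, and CA 19-9 response"), in the endpoint list (4.1) and in the opening of Biostatistics (14.0, "disease control rate (DCR) by both RECIST v1.1 and iRECIST, CA 19-9, and CEA response").

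Section 13.1.7 says how the markers are to be used: "Changes in serial tumor marker measurements, in those patients who have baseline elevations, will be utilized as a surrogate marker of clinical response", with the remaining categories given as "stable disease or disease progression and reported as such".

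Under Secondary objectives in section 14.0, the whole analysis of these markers is one sentence: "CEA and CA 19-9 will be summarized using medians and interquartile range". It does not say whether the quantity is a level or a change, at which time point, or in which patients.

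Table 9 schedules CA 19-9 and CEA at screening, at every cycle from 1 to 9, at even cycles from 10 on, and at discontinuation. No draw is marked in the post-treatment columns.

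**The concern.** The endpoint in 13.1.7 is categorical, rests on change within a patient, and applies only to patients with an elevated baseline. The method in 14.0 summarises a continuous quantity and carries none of these three features. An analyst who follows 14.0 will produce a table from which the secondary endpoint cannot be read.

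The trial's design makes the mismatch matter more than it would in untreated disease. Patients enter with stable or responding disease on platinum (6.1, criterion 1), and those with no evidence of disease may enter (6.1, criterion 6), so some normal baselines are to be expected. Patients with confirmed progression come off treatment, with exceptions (12.1), and marker draws stop with treatment. If the medians are taken of the values at each visit, normal-baseline patients dilute a real fall, and the patients behind each median change over time.

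What is at stake is the interpretability of one descriptive secondary endpoint in each cohort. The Cohort A go/no-go rule and its error rates do not use it.

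**Working it through.** The protocol gives no figure for marker response, so there is none to reproduce. The check has four steps. All marker values and the 50% and 20% cut-offs are assumptions made for illustration; none comes from the protocol.

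**1. Can a median and interquartile range return a response rate?**
Take 15 baseline values: 10, 15, 20, 25, 30, 40, 60, 80, 100, 150, 200, 400, 800, 1500, 3000. The median is the 8th value, 80. The quartiles are (25+30)/2 = 27.5 and (200+400)/2 = 300. Now let the same 15 values recur after treatment, assigned to patients in three ways:

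| Post-treatment assignment | Median | Quartiles | Falls of at least 50% |
|---|---|---|---|
| Every patient unchanged | 80 | 27.5, 300 | 0/15 |
| Each takes the next lower value; the lowest takes the highest | 80 | 27.5, 300 | 3/15 |
| Order reversed | 80 | 27.5, 300 | 6/15 |

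One summary fits three response rates. Reading the sentence as a median of within-patient percent change helps, but does not close the gap. Quartiles of change show only in which quarter (0–25%, 25–50%, 50–75% or 75–100%) the share reaching a cut-off lies. They give neither the proportion nor its interval.

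**2. Does including normal baselines matter?**
Take 8 normal patients (8, 10, 12, 15, 18, 20, 25, 30) and 7 elevated ones (200, 250, 300, 400, 600, 900, 1500). Let every elevated marker fall by 80%, to 40, 50, 60, 80, 120, 180 and 300. The 8th of the 15 ordered values is 30 before and 30 after, so the all-patient median does not move. In the elevated patients alone the median goes from 400 to 400 × 0.2 = 80, and 7/7 respond.

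**3. Does departure from treatment matter?**
Use the baseline set of step 1. Let every marker rise by 10% and the five highest patients leave before the visit. The median of the ten who remain is 1.1 × (30+40)/2 = 38.5, against 80 at baseline, with no responder. In those same ten patients the baseline median was (30+40)/2 = 35, so the paired comparison correctly shows a rise. The artefact belongs to visit-wise values; a within-patient change does not show it. Even with nobody leaving, a uniform 10% fall moves the median from 80 to 72 with no responder at a 20% or a 50% cut-off.

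**4. What precision would a response proportion have?**
The nearest stated figure is the ±25% margin for disease control with 15 patients (14.0). The normal approximation gives 1.96 × √(0.25/15) = 0.253, and the exact interval has a half-width of at most 0.261, so that figure is reproduced. With all 33 patients of Cohort A the approximation is 1.96 × √(0.25/33) = 0.171. If only 7 of 15 were elevated, as in step 2, it would be 1.96 × √(0.25/7) = 0.370. The true denominators are unknown, because the protocol gives no share of elevated baselines.

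**Contrast within section 14.0.** Disease control rate receives a proportion with an exact 95% interval in the same paragraph. For neoantigen and microenvironment measures, the Exploratory objectives state explicitly that change from baseline is summarised. The marker sentence has neither feature.

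**The case against.** The strongest defence is that the two sections are compatible. Section 13.1.7 defines the response use, including change, restriction and categorical reporting; 14.0 adds a descriptive summary; both can be carried out. A numeric cut-off, a confirmation rule and the handling of early leavers are details that a protocol may leave to its SAP.

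Much of this stands. A reader might infer that 14.0 contradicts the restriction in 13.1.7, or that it prescribes medians of marker levels over all patients. The text supports neither. The sentence is silent on population and on level versus change, and omitting a restriction does not negate it. The contrast with the exploratory paragraph makes a reading as levels plausible, but no more. The missing cut-off alone would not be a finding.

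A reader might also want a size for the distortion. Simulations of 33 patients, assuming 30–60% normal baselines, elevated values around 200 U/mL and a median progression-free survival of 7.4 months, give an apparent fall in the week-27 median when no marker changes. That fall is roughly 13–32% if elevated patients progress at twice the hazard, 9–17% at a hazard ratio of 1.5, and zero at 1. The protocol gives no such hazard ratio, no marker distribution and no share of normal baselines. The effect also requires visit-wise levels. These figures show a mechanism and are not evidence about this trial.

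What the defence does not answer is that section 14.0 did choose a statistic for this endpoint, and on no reading does that statistic deliver a response rate. That is a mismatch between method and endpoint rather than a detail deferred.

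**Conclusion.** The point holds in a limited form. Marker response is a named secondary endpoint with a change-based, baseline-elevated definition in 13.1.7, and the analysis fixed in 14.0 cannot yield it. This conclusion follows from the text and from step 1, and needs no assumption about the trial's data. The dilution and attrition effects are conditional: they arise if the medians are taken over visit-wise values that include normal baselines, a form the protocol neither fixes nor rules out. Their size here cannot be stated.

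Severity is low. The endpoint is descriptive, and no sample size, error rate, interim look or decision rule depends on it. The correction is still worth making, because it is cheap and otherwise the endpoint reported may not be the one named.

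**What to change.** Align section 14.0 with 13.1.7, for each marker and each cohort:

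- **Population:** patients with the marker above ULN at baseline. State which draw is baseline, since Table 9 has one at screening and one at Cycle 1.
- **Response:** a within-patient fall from baseline of at least a pre-stated percentage (50%, for example), confirmed at the next scheduled draw. Tie confirmation to the schedule and not to a fixed 3-week interval, because after Cycle 9 draws fall on even cycles, about 6 weeks apart.
- **Analysis:** the proportion responding with an exact 95% confidence interval, counting patients who leave without a confirmed fall as non-responders.
- **Description:** median and interquartile range of within-patient percent change in the same population.

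The cut-offs for the stable and progression categories of 13.1.7 can be placed in the SAP.

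The cost is a few sentences in 13.1.7 and 14.0; all draws are already scheduled. The denominator falls below 33, 15 and 15 by the number of patients with normal baselines, so the interval widens beyond the half-width of up to about 26 points that applies with all 15 patients of Cohort B or C.

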4.2 Intervention

A variety of factors that could potentially predict clinical response to the POLAR regimen will be investigated in peripheral blood and in tumor specimens taken from all participants pretreatment (screening phase), on-treatment, and at the time of disease progression, as outlined in the Treatment and Biospecimen Schema in Figure 1. Data from these investigations will be evaluated for associations with treatment response to POLAR, survival (OS, PFS), and safety (AE).

Research Tissue Collection

All participants will undergo a pre-treatment research biopsy and cfDNA at baseline and during treatment. (Figure 1.) All patients will receive the combination of pembrolizumab 200 mg IV

6

POLAR: a phase 2 trial for pembrolizumab and olaparib maintenance for metastatic PDAC and HRD and/or Exceptional Response to Platinum – Ver. 5/3/2020

every 3 week and olaparib 300 mg twice day orally daily (POLAR) as maintenance therapy. After the first 6 months (9 cycles), on C10D1 Pembrolizumab 400 mg IV every 6 week plus olaparib 300 mg twice a day orally will be continued. At the discretion of the treating investigator, Pembrolizumab 400 mg IV every 6 weeks may begin earlier or Pembrolizumab 200 mg IV every 3 weeks may be continued after C10D1. An on-treatment biopsy (on the 6th- 9th week) and post-progression (before initiation of further therapy) will be obtained where feasible. Biopsies are mandated by protocol baseline and on treatment and at the time of progression except in the setting that there is no disease site that can be safely assessed for biopsy or other clinically relevant safety reason. If tissue acquisition is limited due to availability, available tissues will be prioritized in the following order.

- 1) FFPE (WES, multiplex immunohistochemistry)
- 2) Fresh tissue for single cell analysis with 10-20% cut for organoid culture
- 3) Fresh tissue for single cell analysis
- 4) Fresh frozen for archival

Patients will be presented at multidisciplinary tumor board for discussion related to biopsy safety and site choice were needed. Selected patients with disconcordant and heterogenous response can include up to three different sites for tissue sampling as long as deemed safe.

Research Blood Collection

Peripheral blood mononuclear cells, buffy coat, and plasma will be collected. Circulating tumor DNA on these patients identified as responders and resistant patients will be compared.

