- * Computed Tomography (CT) Chest/abdomen/pelvis with oral and IV contrast or CT chest without contrast AND Magnetic Resonance Imaging (MRI) abdomen/pelvis with contrast if IV contrast/iodine allergy. Imaging frequency every 9-weeks from treatment initiation until Cycle 10, then every 12-week thereafter. If a participant has remained on study for greater than 2 years, imaging can be transitioned to every 3-6 months per MD discretion. Imaging evaluation must be done within +/- 7 days of the planned schedule. Per the treating MD's discretion, imaging can be done before the ontreatment biopsy.
- ** Pembrolizumab 400 mg every 6 weeks will be started on Cycle 10 Day 1. Patients will need to come to clinic during odd cycles post Cycle 10, only if clinically indicated. Per treating investigator's discretion, patients may remain at Pembrolizumab 200 mg IV every 3 weeks after the first 9 cycles. Additionally, to accommodate patients traveling far distances, if, per treating investigator, after the first or second imaging, there are no toxicities, patient's dosing of Pembrolizumab may change to 400 mg IV every 6 weeks. Telehealth visits are allowed.
- 1. **Pre-treatment (baseline) Tumor Tissue:** All patients must submit FFPE tumor tissue (#1 core), fresh tissue (75% of #2 core, #3, and #4 core for scRNAseq and only 25% of #2 core for organoid), and flash frozen tumor tissue (#5, 6, and any extra cores for snRNAseq, whole genome sequencing, and MIBI if possible) as per detailed biomarker management plan (BMP). The goal is to obtain 4-6 cores where clinically safe and feasible at baseline within 2-3 weeks before starting the treatment. In patients participating with major PR or CR may not have enough disease at baseline for multiple biopsies.
- 2. **Tumor Biopsy during Treatment (on-treatment) Period:** Repeat biopsy for on-treatment tumor tissue is requested for study purpose for patients between the 6th to 9th week (+/- 1 week) before the first repeat imaging in the 9th week. Per the treating MD's discretion, imaging can be done before the on-treatment biopsy.
- 3. **Tumor Biopsy at End of Treatment (on progression):** Every effort should be made to obtain EOT (+/- 28 days) biopsies in cases of RECIST v1.1 confirmed disease progression if a patient discontinues study treatment due to disease progression, except in instances where the procedure, as performed in the clinical research setting, poses an unacceptable risk to the patient.

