- **13.1.10. Overall survival (OS):** OS is defined as the time from the initiation of study treatment to the date of death from any cause.

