Wilcoxon rank sum test will be used to assess associations between genetic and transcriptomic signatures at baseline with response while Cox regression will be used to assess associations with PFS and OS. These analyses will be conducted separately for each cohort acknowledging the exploratory nature of these analyses particularly for Cohorts B and C which have limited sample size. Changes between baseline and after treatment in neoantigen induction, TME, and immunomodulatory targets will be summarized descriptively using medians and interquartile range for each cohort separately. To understand the resistance mechanisms, post-treatment changes (4-6 weeks and at progression) of tumor samples and circulating tumor DNA (MSK-ACCESS) from baseline will be associated with response using Wilcoxon rank sum test while Cox regression will be used for PFS and OS outcomes. Finally, in selected patients with viable organoids available from IRB# 15-149 prior to enrollment to POLAR trial, we will concurrently evaluate the response of organoid to POLAR in real time as participants are treated in parallel. Dr. [name] will oversee this part. PFS2 will be estimated using the Kaplan-Meier method. Associations between genetic mutations (HRD and non-HRD) and outcome will be assessed using Fisher's exact test for response and log-rank test for survival outcomes. Biomarkers (reversion mutation, zygosity, plasticity, aneuploidy from tumor, and circulating tumor DNA) will be summarized using proportions. Presence of circulating tumor DNA and levels of CA 19-9 prior to treatment at time points prior to consent and between the consent and start date will be graphically summarized at each timepoint.

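### Cox models relate biomarker change at progression to PFS and OS counted from treatment start, although that change exists only once the PFS event has occurred

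*Protocol*

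**What the plan says.** Protocol 14.0, under the exploratory objectives, sets out how resistance will be studied: "post-treatment changes (4-6 weeks and at progression) of tumor samples and circulating tumor DNA (MSK-ACCESS) from baseline will be associated with response" by the Wilcoxon rank sum test, "while Cox regression will be used for PFS and OS outcomes". The text names no landmark, delayed entry, time-dependent covariate or time origin at progression.

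The clocks are fixed in Protocol 13.1. For PFS (13.1.9): "PFS is defined as the time from the initiation of study treatment to radiographic progression or death". For OS (13.1.10): "OS is defined as the time from the initiation of study treatment to the date of death from any cause". Section 14.0 adds a second PFS origin: "Progression-free survival (PFS) will be analyzed from both the consent date and treatment start date (C1D1), separately". Both origins precede every post-treatment sample.

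On sampling, Protocol 4.2 says: "An on-treatment biopsy (on the 6th- 9th week) and post-progression (before initiation of further therapy) will be obtained where feasible". Table 9 in 11.1 (footnote 2) places the on-treatment biopsy "between the 6th to 9th week (+/- 1 week) before the first repeat imaging in the 9th week". Footnote 3 seeks the end-of-treatment biopsy, within 28 days either side, when RECIST v1.1 progression is confirmed. Footnote 4 ties the on-treatment blood draw to the biopsy date (7 days either side), or to cycle 3 or 4 if there is no biopsy.

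**The concern.** A Cox model asks whether a value known at some time is related to the hazard afterwards. For change at progression the order is reversed: the PFS event has to happen before the covariate can be measured. The model would then describe how the marker differs between patients who progressed early and late, and report it as a hazard ratio for PFS. For OS, patients with a progression sample cannot have died before progression, so part of their survival time is guaranteed by how they entered the analysis.

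At stake is the reading of the resistance objective (Protocol 2.0 and 4.3). Emerging resistance and clonal evolution are processes that may well change with time on treatment, and that is the condition under which this model produces associations with no effect behind them. The analysis text also names a sampling time that does not match the collection schedule, so it is unclear which samples enter.

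**Working it through.** The protocol gives no sample size, power or error rate for this analysis, so there is no stated figure to reproduce.

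**Step 1. What the definitions imply.** Let T be the time from treatment start to radiographic progression, and X the change from baseline at progression.

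- X is observed only if T is observed, so in the PFS model events / patients = 100% and nobody is censored.
- X is measured at about T, or later if treatment continues past RECIST progression (allowed by 10.1 and 12.1). Essentially no PFS follow-up remains after X is known. At each earlier event time, the risk set uses X values that lie in the future.
- OS from treatment start = T + survival after progression. T is guaranteed. If X varies with T, X is associated with OS even when it has no bearing on survival after progression.
- Starting PFS at consent only lengthens the time before X exists.

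**Step 2. Size under no true effect.**

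Inputs from the protocol:
- n = 33 (Cohort A, 14.0).
- Scans every 9 weeks until cycle 10, then every 12 weeks (4.1).
- Median PFS 7.4 months (olaparib arm of the reference maintenance trial, 3.3), or 15.9 months. The latter is the exponential median for the 77% design alternative: 6 × ln 2 / (−ln 0.77) = 4.159 / 0.2614 = 15.9.

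Assumptions not in the protocol:
- Exponential PFS.
- Median survival after progression of 6 months.
- Death without progression exponential with a mean of 60 months.
- Uniform censoring at 12–36 months.
- X = drift × T + standard normal noise, with drift of 0 to 0.2 SD per month.

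Each scenario had 3000 runs of a single-covariate Cox model in progressors, testing at Wald p < 0.05. Entries are median hazard ratio per SD of noise and false-positive rate, for median PFS 7.4 / 15.9 months.

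| Drift (SD/month) | PFS from treatment start | OS from treatment start | OS from progression |
|---|---|---|---|
| 0 | 1.00 / 0.99; 5.0% / 5.4% | 1.00 / 0.98; 5.0% / 5.3% | 1.00 / 0.99; 5.1% / 4.2% |
| 0.05 | 0.74 / 0.70; 27.9% / 23.9% | 0.81 / 0.76; 12.3% / 13.2% | 1.00 / 1.00; 4.8% / 4.2% |
| 0.1 | 0.60 / 0.55; 70.3% / 65.0% | 0.74 / 0.66; 26.5% / 31.9% | 1.01 / 0.99; 4.9% / 4.5% |
| 0.2 | 0.47 / 0.42; 99.0% / 96.5% | 0.69 / 0.64; 57.5% / 52.9% | 1.00 / 1.00; 5.3% / 5.0% |

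Hazard ratios fall below 1 because, with upward drift, a larger change goes with later progression. Downward drift would reverse the direction.

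**Step 3. If patients without a progression sample are kept and coded as unchanged.** With a binary change present at random in half of the progressors, PFS gave hazard ratios of 1.45–1.48 (13–15% false positives) at a median of 7.4 months and 2.21–2.25 (40–42%) at 15.9 months. OS from treatment start gave 1.00–1.02 (4–5%) and 1.30–1.36 (7–8%). This coding makes PFS false-positive even without drift, because only patients with the event can be coded as changed.

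**Step 4. Sampling weeks.** The analysis text says weeks 4–6. The biopsy window is weeks 6–9, or 5–10 with its tolerance, so the two share weeks 5–6. Blood within 7 days of the biopsy can fall in weeks 4–11. The overlap is partial.

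**The case against.** The strongest case against is that this is one compressed sentence about an exploratory aim. Time origins and covariate handling for such models are commonly left to the SAP, which is not at hand. The sentence promises association rather than prediction, and the inflation in Step 2 depends on assumed drift, with about 5% false positives in progressors when drift is zero. All of that is fair, and it limits the weight of the point. It does not remove it. An SAP could move the OS origin, but the protocol itself pairs at-progression change with PFS, and no SAP detail can create PFS follow-up after the event. Nor can absence of drift be presumed in a trial that sets out to study evolving resistance.

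A reader might infer that the on-treatment change has the same fault, so that its hazard ratios carry immortal-time bias. The documents do not support this. Everyone in that model has the sample, so no group has guaranteed time that another lacks. For patients who are all event-free at a landmark, moving the Cox origin leaves the partial likelihood unchanged. In the simulation the model from treatment start gave hazard ratios of 0.99–1.01 and 4.7–5.9% false positives, against 4.7–6.0% with entry delayed to the sample.

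A reader might also compute that about a fifth of patients are lost before sampling: 1 − 0.53^(9/26.09) = 20% by week 9. That takes the null rate and continuously observed progression; the 77% alternative gives 1 − 0.77^(9/26.09) = 9%. Under the protocol, the first scheduled scan is at week 9 (7 days either side), and the biopsy normally precedes it, so few PFS events would be recorded first. Some selection of patients who reach and tolerate a biopsy remains, but a week-10 landmark would keep that selection and discard patients who progress at the first scan.

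**Conclusion.** The point holds for the sample at progression. For PFS the defect is structural and follows from the protocol's own definitions: the covariate exists only in patients who have progressed, and nothing remains to model. For OS from treatment start, the time to progression is guaranteed survival, and starting the clock at progression cures it.

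The size is conditional. At a drift of 0.05–0.2 SD per month, false-positive rates were 24–99% for PFS and 12–58% for OS; with no drift they stayed at about 5%. These figures rest on the assumed drift, survival after progression, censoring and coding, and should be read as a range of illustration.

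The sampling weeks disagree in part, which is a smaller matter of wording. Severity is low: no primary or secondary endpoint and no Cohort A decision rule is touched.

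**What to change.** In Protocol 14.0, exploratory objectives:

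1. Remove PFS as a Cox outcome for change at progression. Report that change descriptively; if it is set against time on treatment, present that as description only.
2. Relate change at progression to OS counted from the progression date or the progression sample. The sample date is the cleaner origin where sampling follows progression by some weeks.
3. Reconcile the week 4–6 time point in 14.0 with the biopsy window in 4.2 and Table 9 footnote 2, and with the blood timing in footnote 4, so that one definition says which samples enter.

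The on-treatment change needs no landmark on these grounds.

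The cost is wording only. No sample or visit is added. No deaths are lost from the OS analysis, because every death among patients with a progression sample falls after that sample. What is given up is a PFS hazard ratio that could not have been interpreted.
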